10 DATA COLLECTION AND QUALITY ASSURANCE

10.1 Data Collection Forms

We will collect data on the Revised Memory and Behavior Problem Checklist and the Preparedness for Caregiving Scale via a REDCap survey. We will deliver a link to the survey via an email or text message. Caregivers will be instructed to follow the link and complete the survey.

We will collect data on the System Usability Scale via a REDCap survey. We will deliver a link to the survey via an email or text message. Caregivers will be instructed to follow the link and complete the survey.

We will collect qualitative data during exit interviews that will be conducted by [name], [name], and/or [name]. The interviews will be audio recorded, and we will also take notes during and after the interview.

10.2 Data Management

Data collection and management will be the responsibility of the University of Washington. All data collected from participants will be labeled with a unique study identification number and not the participant's name or any other information that could

identify the participant. Only the study identification number will appear on data records and computer files. The contact information of study participants will be kept in a password-protected file and computer. All data collected from participants will be kept confidential and accessible only by [name], [name], and [name] at the University of Washington. [name] will view only summaries of aggregated data. We will not use participants names in reports of study findings, REDCap surveys, or audio recordings of interviews. Instead, we will label everything with the study identification number. We will destroy data that identifies participants when we have finished recruitment. We plan to keep de-identified data indefinitely.

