6 STUDY PROCEDURES

6.1 Schedule of Evaluations

Assessment	Screening Assessment (Week 0)	Baseline Assessment (Week 0)	Module Assessments (Weeks 1-6)	Final Assessment (Weeks 7-8)
Inclusion/Exclusion Criteria	X			
Informed Consent Form	X			
Enrollment	X			
Sociodemographic characteristics		X		
Revised Memory and Problem Behavior Checklist		X		X
Preparedness for Caregiving Scale		X		X
Perceived Usability of Modules			X	
Qualitative Assessment of Intervention Acceptance				X

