6.2 Description of Evaluations

6.2.1 Screening Assessment

For caregivers who are interested in study participation, the study staff members will schedule a phone call to answer any questions they may have and screen for eligibility. Study staff will use a structured screening survey to ask potential participants their age, whether they live with PLWD or within 5 miles, the number of hours of care they provide each week, their race/ethnicity, and whether PLWD lives in assisted living or skilled nursing facilities.

We will email an e-consent form to caregivers who are eligible. After emailing these materials, study staff will contact caregivers by phone again to review the e-consent form and answer any questions. Caregivers will be instructed to sign the e-consent form. Enrollment will begin when the study staff members receive the e-consent forms signed by caregivers.

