6.2.4 Final Assessment

After 6-8 weeks post-enrollment, caregivers will receive an email or text message asking them to complete the REDCap baseline survey that contains:

- Revised Memory and Problem Behavior Checklist
- Preparedness for Caregiving Scale

In addition, study staff members will schedule an exit interview with participants. The interview will happen virtually (phone or videoconferencing) and will be under 1 hour. We will ask participants semi-structured questions to gauge their acceptance of the online learning modules and their experience completing the REDCap survey.

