9.4 Outcomes

9.4.1 Primary outcome

The primary outcomes are: (1) Revised Memory and Behavior Problem Checklist and (2) Preparedness for Caregiving Scale. We will collect these outcomes at baseline and 6-8 weeks post-enrollment via a REDCap survey.

- 1. Revised Memory and Behavior Problem Checklist.**^{27,28} Caregivers will rate memory, depression, and disruptive behavior problems in the PLWD. The instrument contains 24 items (7 memory-related, 8 depressive, and 9 disruptive) that assess problem behaviors and are rated for frequency of occurrence during the past week and caregiver reaction to the problem behaviors.
- 2. Preparedness for Caregiving Scale.**²⁹ Caregivers will rate how prepared they are for various aspects of caregiving. The instrument contains 8 items that ask caregivers how well prepared they believe they are to provide physical care, emotional support, deal with the stress of caregiving, and set up in-home support services. Each item is rated on a 5-point scale ranging from 0 (not at all prepared) to 5 (very well prepared).

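### Section 10.2 destroys identifying data at the end of recruitment, although caregivers enrolled in the preceding 6-8 weeks still have to be reached for the final survey and exit interview

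*Combined protocol and SAP*

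**What the plan says.** Section 10.2 (Data Management) sets one trigger for destroying identifiers: "We will destroy data that identifies participants when we have finished recruitment". De-identified data are kept indefinitely. On how the data are held, the same section says "Only the study identification number will appear on data records and computer files" and "The contact information of study participants will be kept in a password-protected file and computer". It gives the contact file no retention period of its own.

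The follow-up plan is set out elsewhere:

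- **Start of the clock (Section 6.2.1).** "Enrollment will begin when the study staff members receive the e-consent forms signed by caregivers".
- **Primary outcomes (Section 9.4.1).** For the behavior checklist and the preparedness scale: "We will collect these outcomes at baseline and 6-8 weeks post-enrollment via a REDCap survey".
- **Route.** Section 6.2.4: "After 6-8 weeks post-enrollment, caregivers will receive an email or text message". Section 10.1: "We will deliver a link to the survey via an email or text message". The schedule in Section 6.1 puts this final assessment in weeks 7-8.
- **Exit interview (Sections 3 and 6.2.4).** Scheduled after 6-8 weeks and held by phone or videoconference.
- **Safety and discontinuation.** Adverse events are picked up through staff contact during research activities (Section 7.2.3). Caregivers who discontinue are followed if they permit it (Section 8).

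Section 9.3 allocates 4 months of the 12-month study to recruitment, with a maximum of 20 caregivers (Section 9.2).

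**The concern.** The destruction rule is tied to the wrong milestone. Recruitment ends when enrollment stops; the need for contact details ends when the last enrolled caregiver has finished follow-up, 6-8 weeks or more later.

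If the sentence is followed literally while anyone is still in follow-up, staff cannot send those caregivers the final survey link or arrange the interview. They lose the second measurement of both primary outcomes and the interview data on acceptance and on the REDCap survey experience. Because data records carry only the study number, destroying the link between number and person would also hinder matching a follow-up record to its baseline. Destroyed identifiers cannot be recovered.

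If staff instead keep the file so that follow-up can continue, they depart from a written confidentiality commitment, and Section 10.3.4 has deviations logged. Whenever someone is in follow-up at closing, Section 10.2 and the follow-up sections cannot both be obeyed.

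The effect on safety is indirect. No contact is scheduled specifically for adverse events, so losing the other contacts removes the occasions on which events would be noticed.

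**Working it through.** The plan states no figure for this point, so there is none to reproduce. The check is a comparison of dates, followed by an illustration of size.

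**Order of events for one caregiver**

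| Event | Timing | Needs contact details or the ID link? |
|---|---|---|
| Signed consent received; enrollment (6.2.1) | day 0 | yes |
| Baseline survey link (6.2.2, 10.1) | after consent | yes |
| Final survey link, both primary outcomes (6.2.4, 9.4.1, 10.1) | 6-8 weeks; weeks 7-8 in 6.1 | yes |
| Exit interview arranged (3, 6.2.4) | after 6-8 weeks | yes |
| Identifiers destroyed (10.2) | end of recruitment | – |

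For a caregiver enrolled less than 6-8 weeks before recruitment closes, the last row comes before the two rows above it. Module access is left out of the argument: Section 3 has modules sent by text or email, but Section 5.2 describes login with an email address and the caregiver's own password, so access may not depend on the study's contact file.

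**Inputs**

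- Recruitment window T = 4 months (Section 9.3) = 4 × 365.25/12 = 121.75 days, or 17.4 weeks.
- Follow-up w = 42 days (6 weeks), 49 days (7 weeks, the start of the Section 6.1 window) or 56 days (8 weeks).
- Maximum sample size 20 (Section 9.2).
- Accrual pattern: not given. Even accrual of 20 caregivers over the full window is assumed for illustration only.

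**Formulas.** The latest enrollment that reaches its final-assessment date by closing is T − w. Under even accrual, the share still in follow-up at closing is w/T.

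| w | T − w | Share w/T | Of 20 |
|---|---|---|---|
| 42 days | 79.75 days (week 11.4) | 42/121.75 = 0.345 | 6.9 |
| 49 days | 72.75 days (week 10.4) | 49/121.75 = 0.402 | 8.0 |
| 56 days | 65.75 days (week 9.4) | 56/121.75 = 0.460 | 9.2 |

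**Range**

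- *Floor.* If recruitment stays open for the full 4 months and nobody enrolls after about week 9.4 (8-week follow-up) or week 11.4 (6-week follow-up), no one is affected.
- *If recruitment counts as finished on the day the last caregiver enrolls,* at least that one caregiver is affected.
- *Even accrual of 20 over 4 months.* About 7-9 of 20; on the week 7-8 timing in Section 6.1, about 8-9 of 20.
- *Faster accrual.* If the target were filled evenly in less than 4 months and recruitment then closed, T would be shorter and w/T larger.

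**After the change.** Keeping identifiers until the last enrollee reaches 6-8 weeks moves destruction to 17.4 + 6 = 23.4 weeks up to 17.4 + 8 = 25.4 weeks from the start of recruitment (about 5.4-5.8 months), plus the time needed to complete the interview.

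**The case against.** The best counter-argument is that nobody would carry out the sentence literally. Section 10.3.3 provides a log of survey prompts and interview scheduling that is reviewed weekly, Section 7.2.3 has weekly staff meetings, and Section 10.3.5 has compliance monitoring. Staff would see open follow-up before deleting anything. That makes accidental loss less likely, but it leaves the rule unchanged: keeping the file would still be a departure from the protocol.

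A second argument is that the sentence may mean only recruitment or screening records, such as the screening log in Section 4.3. This reading is possible but fits poorly. The sentence speaks of participants, whereas Sections 4.3 and 6.2.1 describe people not yet enrolled as potential participants. It also sits in the paragraph that describes the participants' contact file. The sentence after it deals with de-identified data, leaving no third category for a contact list or link kept longer.

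Three smaller points stand. The consent pages were not available to us, so any retention wording there could not be checked. The 34-46% figure depends on an accrual pattern and closing date that the documents do not state. The firm conflict is with the final survey and exit interview; the adverse event and post-discontinuation contacts are, respectively, incidental to other activities and conditional on permission.

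**Conclusion.** The concern holds. As written, Section 10.2 conflicts with Sections 3, 6.2.4, 9.4.1 and 10.1 for every caregiver still in follow-up when recruitment finishes. Confidence in the contradiction within the supplied text is high.

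The number of caregivers affected cannot be derived from the documents. It may be 0; about 7-9 of 20 is an illustration that rests on even accrual of 20 people over exactly 4 months.

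The consequence is bounded. The pilot tests no hypotheses and its quantitative analysis is descriptive (Sections 9.1 and 9.5), so no error rate or power figure changes. What could be lost is follow-up and interview information from some of at most 20 caregivers, in a study whose purpose is to try out the modules and the two-time-point survey. The loss is irreversible and easily prevented, so the sentence should be corrected, although it is probably only a drafting slip.

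**What to change.** Replace the sentence in Section 10.2 with wording such as: *Identifying data, including the link between contact details and study number, will be destroyed after the last participant's final survey, exit interview and any required adverse event follow-up are complete.* If the consent form repeats the current rule, align it.

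In the same edit, state whether the signed e-consent forms documented in REDCap (Section 11.2) fall under this rule or have their own retention period, since they also identify participants.

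The cost is one sentence in the protocol and possibly one in the consent form. Identifiers would be held about two months longer in the same password-protected file, somewhat more if the last interview or adverse event follow-up runs late.

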10.3 Quality Assurance

10.3.1 Training

As is the case with all investigators, key personnel, and all those responsible for the design and conduct of research at the University of Washington, [name], [name], and [name] have received training on the protection of human subjects. [name] will be responsible for training study staff members on the study protocol.

10.3.2 Quality Control Committee

This study will not utilize a quality control committee.

10.3.3 Metrics

We will use a log to document whether and when caregivers enrolled in the study were prompted to complete outcome assessments via the REDCap survey. The log will also document whether and when an exit interview has been scheduled. We will review the log on a weekly basis.

10.3.4 Protocol Deviations

We will use a protocol deviation log. The log will enable us to capture a description of the protocol deviation, the deviation category (e.g., safety, informed consent, eligibility, protocol implementation), date the deviation occurred, and date the institutional review board was notified.

10.3.5 Monitoring

[name] will be responsible for regularly monitoring all aspects of the study to assure protocol compliance, data quality, etc.

11 PARTICIPANT RIGHTS AND CONFIDENTIALITY

11.1 Institutional Review Board (IRB) Review

This protocol and the informed consent document and any subsequent modifications will be reviewed and approved by the IRB responsible for study oversight.

11.2 Informed Consent Form

Consent forms in English and Spanish will be IRB-approved and the participant will be asked to read and review the document. Using the language preferred by participants (English or Spanish), the study staff member will explain the research study to the participant and answer any questions that may arise. A verbal explanation will be provided in terms suited to the participant's comprehension of the purposes, procedures, and potential risks of the study and of their rights as research participants. Participants will be informed that participation is voluntary and that they may withdraw from the study at any time, without prejudice, and that the quality of their medical care will not be adversely affected if they decline to participate in this study. Participants will have the opportunity to carefully review the electronic consent form and ask questions prior to signing. The participants will be given a copy of the informed e-consent form so that they may discuss the study with their family or surrogates or think about it prior to agreeing to participate. The informed e-consent process will be conducted and documented in REDCap (including the date), and the form e-signed, before the participant undergoes any study-specific procedures. A copy of the signed informed e-consent document will be sent to the participants for their records.

11.3 Participant Confidentiality

Any data, forms, reports, audio recordings, and other records will be identified only by a participant identification number to maintain confidentiality. All records will be kept in a locked file cabinet. All computer entry and networking programs will be done using participant identification numbers only. Information will not be released without written permission of the participant, except as necessary for monitoring by IRB, the FDA, the NIA, and the OHRP.

11.4 Study Discontinuation

The study may be discontinued at any time by the IRB, the NIA, the OHRP, the FDA, or other government agencies as part of their duties to ensure that research participants are protected.

16 SUPPLEMENTS/APPENDICES

I. Outcome Measures

Revised Memory and Behavior Checklist

Instructions: The following is a list of problems patients sometimes have. Please indicate if any of these problems have occurred during the past week. If so, how much has this bothered or upset you when it happened Use the following scale for your reaction. Please read the description of the ratings carefully.

Has it occurred in the past week:

0 = No
1 = Yes

Reaction Ratings:

0 = not at all
1 = a little
2 = moderately
3 = very much
4 = extremely

Please answer all the questions for both frequency and reaction.

(RC11)

Problem	Has it occurred? (in past week)		Reaction (how much it bothered you)
1. Asking the same question over and over	NO	YES	
2. Trouble remembering recent events (i.e. items in newspaper or TV)	NO	YES	
3. Trouble remembering significant past events	NO	YES	
4. Losing or misplacing things	NO	YES	
5. Forgetting what day it is	NO	YES	
6. Starting, but not finishing, things	NO	YES	
7. Difficulty concentrating on a task	NO	YES	
8. Destroying property	NO	YES	
9. Doing things that embarrass you	NO	YES	
10. Waking you or other family members up at night	NO	YES	
11. Talking loudly and rapidly	NO	YES	
12. Appears anxious or worried	NO	YES	
13. Engaging in behavior that is potentially dangerous to self or others	NO	YES	
14. Threats to hurt oneself	NO	YES	
15. Threats to hurt others	NO	YES	
16. Aggressive to others verbally	NO	YES	
17. Appears sad or depressed	NO	YES	
18. Expressing feelings of hopelessness or sadness about the future	NO	YES	
19. Crying and tearfulness	NO	YES	
20. Commenting about death of self or others	NO	YES	
21. Talking about feeling lonely	NO	YES	
22. Comments about feeling worthless or being a burden to others	NO	YES	
23. Comments about feeling like a failure, or about not having any worthwhile accomplishments in life	NO	YES	
24. Arguing, irritability, and/or complaining	NO	YES	

The Preparedness for Caregiving Scale

YOUR PREPARATION FOR CAREGIVING

We know that people may feel well prepared for some aspects of giving care to another person, and not as well prepared for other aspects. We would like to know how well prepared you think you are to do each of the following, even if you are not doing that type of care now.

	Not at all prepared	Not too well prepared	Somewhat well prepared	Pretty well prepared	Very well prepared
1. How well prepared do you think you are to take care of your family member's physical needs?	0	1	2	3	4
2. How well prepared do you think you are to take care of his or her emotional needs?	0	1	2	3	4
3. How well prepared do you think you are to find out about and set up services for him or her?	0	1	2	3	4
4. How well prepared do you think you are for the stress of caregiving?	0	1	2	3	4
5. How well prepared do you think you are to make caregiving activities pleasant for both you and your family member?	0	1	2	3	4
6. How well prepared do you think you are to respond to and handle emergencies that involve him or her?	0	1	2	3	4
7. How well prepared do you think you are to get the help and information you need from the health care system?	0	1	2	3	4
8. Overall, how well prepared do you think you are to care for your family member?	0	1	2	3	4
9. Is there anything specific you would like to be better prepared for? _____					

MEAN SCORE of the number of items answered: _____					

Reprinted with permission from author.

Stewart & Archbold (1986, 1994)

System Usability Scale

Instructions: For each of the following statements, mark one box that best describes your reactions to the website today.

		Strongly Disagree				Strongly Agree
1.	I think that I would like to use this website frequently.					
2.	I found this website unnecessarily complex.					
3.	I thought this website was easy to use.					
4.	I think that I would need assistance to be able to use this website.					
5.	I found the various functions in this website were well integrated.					
6.	I thought there was too much inconsistency in this website.					
7.	I would imagine that most people would learn to use this website very quickly.					
8.	I found this website very cumbersome/awkward to use.					
9.	I felt very confident using this website.					
10.	I needed to learn a lot of things before I could get going with this website.					

Please provide any comments about this website:

II. Demographics Questionnaire

What is your age? * must provide value
	 years old

What is your current occupational status? * must provide value
	
 Employed  Unemployed  Homemaker  Student  Retired  Disabled  Other
 
reset

Do you work outside your home?
	
 Yes  No
 
reset

Who are the people living in your home?
	
 Partner or father of child  Children, related or unrelated, such as newborn babies, grandchildren, or foster children  Relatives, such as adult children, cousins, or in-laws  Nonrelatives, such as roommates or live-in babysitters  People staying here temporarily  None of the above
 
Mark all that apply.

What is the highest grade or level of schooling you completed? * must provide value
	
 Less than 8 years  8 through 11 years  12 years or completed high school  Post high school training other than college (vocational or technical)  Some college  College graduate  Postgraduate
 
reset

How well do you speak English? * must provide value
	
  Very well  Well  Not well  Not at all 
 
reset


What language do you prefer to speak? * must provide value
	
  English  Spanish  Other 

What language(s) do you speak at home? * must provide value
	
  English  Spanish  Other 

Are you of Hispanic, Latino/a, or Spanish origin? * must provide value
	
  No, not of Hispanic, Latino/a, or Spanish origin  Yes 
 
reset

What is your race? * must provide value
	
  White  Black or African American  American Indian or Alaska Native  Asian Indian  Chinese  Filipino  Japanese  Korean  Vietnamese  Other Asian  Native Hawaiian  Guamanian or Chamorro  Samoan  Other Pacific Islander  Other, specify 
 
One or more categories may be selected.

What is your gender? * must provide value
	
  Female  Male  Other 
 
reset

Thinking about members of your family that live in your household, what is the combined annual income, meaning the total pre-tax income from all sources earned in the past year?

* must provide value

- \$0 to \$9,999
- \$10,000 to \$14,999
- \$15,000 to \$19,999
- \$20,000 to \$34,999
- \$35,000 to \$49,999
- \$50,000 to \$74,999
- \$75,000 to \$99,999
- \$100,000 to \$199,999
- \$200,000 or more
- don't want to disclose

[reset](#)

Do you own a smartphone, tablet, laptop or computer?

* must provide value

- Smartphone
- Tablet
- Laptop
- Computer
- None

Do you or any member of your household have access to the Internet using a:

- cellular data plan for a smartphone or other mobile device?
- broadband (high speed) Internet service such as cable, fiber optic, or DSL service installed in this household?
- satellite Internet service installed in this household?
- dial-up Internet service installed in this household?
- some other service?

Is the person with dementia currently covered by any of the following types of health insurance or health coverage plans?

* must provide value

- Insurance through a current or former employer or union (you or another family member)
- Insurance purchased directly from an insurance company (by you or another family member)
- Medicare, for people 65 and older, or people with certain disabilities
- Medicaid, Medical Assistance or any kind of government-assistance plan for those with low incomes or a disability
- TRICARE or other military health care
- VA (enrolled for VA health care)
- Indian Health Service
- Other

Are you currently covered by any of the following types of health insurance or health coverage plans?

* must provide value

- Insurance through a current or former employer or union (you or another family member)
- Insurance purchased directly from an insurance company (by you or another family member)
- Medicare, for people 65 and older, or people with certain disabilities
- Medicaid, Medical Assistance or any kind of government-assistance plan for those with low incomes or a disability
- TRICARE or other military health care
- VA (enrolled for VA health care)
- Indian Health Service
- Other

What is your relationship to the person with Alzheimer's disease or related dementia?

* must provide value

- Spouse or partner
- Parent
- Close family member
- Friend or other non-relative
- Other

[reset](#)

How old is the person with Alzheimer's disease or related dementia?
 
* must provide value
	 years old

What is the gender of the person with Alzheimer's disease or related dementia?
 
* must provide value
	 Female  Male  Other reset

How long have you been in the caregiving role?
 
* must provide value
	 years

Do you live in the same household as the person with Alzheimer's disease or related dementia?
 
* must provide value
	 Yes  No reset

Thinking of all the kinds of help you provide for this person, about how many hours do you spend in an average week providing care?
 
* must provide value
	 Less than 5 hours per week  5-14 hours per week  15-20 hours per week  21-34 hours per week  35 or more hours per week reset

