Caregivers will complete a baseline survey using a REDCap link that will be delivered to caregivers via email or text message. The survey will include sociodemographic characteristics and the outcome measures (i.e., Revised Memory and Problem Behavior Checklist and Preparedness for Caregiving Scale). We will collect outcome measures from caregivers again 6-8 weeks post-enrollment using the same data collection method. Sociodemographic characteristics will include: caregiver age, occupational status, whether caregiver works outside of the home, number of people living in caregiver’s home, educational attainment, English fluency, preferred language, languages spoken at home, race, gender, annual household income, device ownership, Internet access at home, health insurance status of caregiver and PLWD, relationship to PLWD, age of PLWD, gender of PLWD, number of years in caregiving role, whether caregiver lives in same household as PLWD, and hours per week providing care.

After completing the baseline survey, caregivers will begin participation in the intervention. ***The intervention tested in this study will only involve the self-directed training component of the STAR-VTF intervention.*** We will provide caregivers with the video modules via text message or email. We will also mail each participant a copy of the adapted version of the STAR-VTF workbook in their preferred language. There are handouts and resources to along with each lesson. Caregivers will be instructed to complete 1 module per week for 7 weeks (Table 2).

After 6-8 weeks, we will schedule an exit interview with caregivers. The interview will happen virtually (phone or videoconferencing) and will be under 1 hour. We will ask participants semi-structured questions to understand their experience with the online training modules and with completing the survey via REDCap.

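### The two required health-insurance items have no uninsured answer, so the planned insurance descriptor cannot record anyone as uninsured

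*Combined protocol and SAP*

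**What the plan says.** Section 3 (Objective 2) plans to describe participants by, among other things, "health insurance status of caregiver and PLWD". Section 16, part II (Demographics Questionnaire) has two items for this. One asks "Is the person with dementia currently covered by any of the following types of health insurance or health coverage plans"; the other asks "Are you currently covered by any of the following types of health insurance or health coverage plans". Each carries the flag "must provide value". Both show the same eight choices: employer or union insurance, directly purchased insurance, Medicare, Medicaid or similar, TRICARE or other military care, VA, Indian Health Service, and *Other*.

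Section 6.2.2 places this questionnaire in the same REDCap baseline survey as the Revised Memory and Problem Behavior Checklist and the Preparedness for Caregiving Scale, which section 9.4.1 names as the primary outcomes. Section 3 then says: "After completing the baseline survey, caregivers will begin participation in the intervention". Insurance is not an eligibility criterion in sections 4.1 and 4.2, so uninsured caregivers, and caregivers of uninsured people, can enrol.

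**The concern.** Both questions ask whether the person holds any of the listed kinds of coverage. For someone with none, the honest reply is no. The form has no box for that, and the required flag rules out a blank. The remaining choices are a named plan the person does not have, or *Other*, which after that question reads as some other plan.

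What is at stake is one planned descriptor. The protocol's rationale rests on barriers to care for Latino families (section 2.1) and mentions the lack of affordable services (section 2.2). Readers of the pilot will want to know how many participants lacked insurance, and the form cannot tell them. The item about the person with dementia has a second gap: the caregiver answers for someone else and may not know.

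**Working it through.** The plan states no figure to reproduce. The sample size of up to 20 is pragmatic (section 9.2), no hypothesis is tested (section 1.1) and the quantitative analysis is descriptive (section 9.5). The check is of the form itself.

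**Step 1: compare items within the questionnaire.**

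| Item | Marked required | Answer for none or opt-out |
|---|---|---|
| Insurance, person with dementia | Yes | None |
| Insurance, caregiver | Yes | None |
| Device ownership ("Do you own a smartphone, tablet, laptop or computer") | Yes | *None* is offered |
| Household income | Yes | "don't want to disclose" is offered |
| People living in the home | No | *None of the above* is offered |
| Household Internet access | No | None |

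Three other items give the respondent a way out, so the gap in the insurance items looks like an oversight. Both insurance lists appear complete and end in the same *Other*, so an option lost in reading the file is unlikely.

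**Step 2: follow an uninsured respondent through the item.** No option means uninsured, so the number recorded as uninsured is 0 and the recorded share is 0/n = 0% for any n and any true rate.

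**Step 3: ask whether the status can be recovered.** The count under *Other* is the uninsured who tick it plus those with unlisted coverage. One count cannot be split into two unknowns. No text field is printed beside *Other* on these items, although the race item has a choice that asks for specification. Nothing else in the questionnaire asks about coverage.

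**Step 4: scale, for illustration only.** The documents give no uninsured rate. Let p be an assumed share of uninsured caregivers, with n = 20 (section 9.2) or n = 5 (the accrual threshold in section 9.3). The expected number is n × p. Treating caregivers as independent, the chance of at least one is 1 − (1 − p)^n.

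| Assumed p | Expected, n = 20 | At least one, n = 20 | Expected, n = 5 | At least one, n = 5 |
|---|---|---|---|---|
| 5% | 1 | 64% | 0.25 | 23% |
| 10% | 2 | 88% | 0.5 | 41% |
| 20% | 4 | 99% | 1 | 67% |
| 30% | 6 | 99.9% | 1.5 | 83% |

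For example, at p = 10% and n = 20, 1 − 0.90^20 = 0.878. These figures concern the caregiver item only; no range is offered for the person with dementia.

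**The case against.** The best defence is that little depends on this variable. The study is a single-arm descriptive pilot without hypotheses or subgroup analyses. Insurance is neither an outcome nor an eligibility criterion, and it would fill one row or so of a baseline table. That stands, and it limits the weight of the point. It does not make the row correct.

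A second defence is that piloting will expose awkward items, because the exit interview asks about completing the REDCap survey (sections 3 and 6.2.4). That may help later studies. It comes 6-8 weeks after enrolment, when this study's insurance answers have already been recorded.

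A reader might also infer three stronger things:

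- **That uninsured caregivers are stopped at a required field, and the baseline of both primary outcomes is lost.** The survey is shared and precedes the modules, so the inference is natural. But *Other* can always be selected, and a caregiver who selects it still submits both scales. The documents do not describe how required fields are enforced, how pages are ordered or whether partial answers are saved. Abandonment is possible but not shown.
- **That Objective 3 is undermined.** Section 3 (Objective 3) names only the two outcome scales as content of the instrument for future studies. The demographic items are in the baseline survey being piloted, but the documents do not say that they will be carried forward.
- **That the Internet item fails in the same way.** The item "Do you or any member of your household have access to the Internet using a" is not marked required and shows no answer for none, so a blank could mean no access or a skipped question. But respondents reach the survey through an online link, and the choices include mobile data and some other service. Few are likely to have no household access, and the item's exact response format cannot be confirmed from the text. This is a much weaker point.

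**Conclusion.** The point holds as a minor defect in a baseline descriptor. As printed, both required insurance items make it impossible to record a caregiver or a person with dementia as uninsured. The reported uninsured share would be 0% by construction, and the survey data could not correct it. That conclusion needs no assumption beyond the form being fielded as printed.

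The number affected does rest on an assumption: 1 to 6 of 20 caregivers if the uninsured share is between 5% and 30%. It should not be cited as an estimate for this population. No sample size, error rate or outcome analysis changes.

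**What to change.** Add *None / not currently insured* and *Don't know* to both insurance items, in the English and Spanish versions, before the first baseline survey is sent. If baseline surveys have already been completed, report *Other* as including people who may be uninsured, and do not report an uninsured percentage from those records.

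Optionally, add *None of these* to the Internet-access item, so that lack of access is a positive answer and not a blank.

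The cost is a few response options in REDCap, their translation and a minor update of the form with the IRB. Participants face no extra questions.
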